## Protocol

### 1. Project Title:

A pilot study investigating the effects of vibrotactile stimulation (Not Impossible Vibrohealth) on motor control and symptoms in patients with movement disorders

### 3. Abstract:

Non-invasive vibrotactile stimulation (VTS) of the skin has long been reported anecdotally to potentially improve motor control and reduce the motor symptoms of patients with movement disorders including Parkinson's disease. Though few rigorously controlled clinical trials have been performed on the effects of VTS, devices that provide VTS have received significant media attention as potential non-medical interventions for movement disorders. In this study, we will test the effect of VTS applied non-invasively to patients with movement disorders to determine if there are any beneficial effects of VTS on common tasks of motor control and/or abnormal motor symptoms in patients with PD, essential tremor (ET), and dystonia.

### 4. Background:

Movement disorders can be defined as neurologic syndromes in which there is either an excess or paucity of voluntary and/or automatic movements that is not due to weakness or spasticity. A prototypical example is Parkinson's disease (PD), a chronic progressive neurodegenerative disorder characterized by rigidity, bradykinesia, gait and/or postural instability, and resting tremor.  The classical PD tremor has a dominant frequency of 3–6Hz and is most often present at rest in the upper extremities of the affected subjects. Other movement disorders include essential tremor (ET, in which tremor is

predominantly present with action) and dystonia (in which tremor is associated with a syndrome of abnormal muscle contractions resulting in involuntary movements and postures). Although medical and surgical therapies are available for the symptomatic treatment of these movement disorders, current treatment options can produce significant side effects and often provide incomplete benefit for the motor symptoms of these diseases. Therefore, continued investigation of new potential treatment options is an important priority.

The application of external non-invasive vibrotactile stimulation (VTS) of the skin as a therapeutic intervention for movement disorders has been of interest since the 19th century, when Jean-Martin Charcot anecdotally observed a relief of symptoms following the use of a vibrating chair in patients with PD. Since then, whole body vibrating massage has been investigated as a potential means to reduce the symptoms of PD, however results have been inconsistent. Similarly, devices that provide VTS have been investigated in small studies for the amelioration of symptoms of essential tremor and dystonia, with only limited conclusions possible to date due to sample size and study design limitations.

At the current time, it is estimated that at least 1 in 5 adults use at least one wearable health-related technology, and wearable devices intended to track the symptoms of PD are already in clinical use. Wearable devices that provide VTS (such as the as the Vibrohealth system recently developed by Not Impossible Labs, <https://www.youtube.com/watch?v=G7T53xN1lqI>) have received significant attention in the lay press and within patient support groups. As more and more wearable devices (which may be marketed directly to patients) are developed, it will be critically important for academic clinical researchers to participate in testing the efficacy of these devices in rigorous clinical trials. This need for independent study has been recognized by the Parkinson's Foundation (PF), which has selected the University of Florida as a research site tasked with determining the optimal device settings and testing the Not Impossible Vibrohealth system as an adjunctive therapy for movement disorders. We will accomplish this through the following specific aims.

## **5. Specific Aims:**

**Specific Aim. Evaluate the feasibility, reliability, and clinical effects of VTS on basic tasks of motor control and on the motor symptoms of patients with movement disorders.**

Hypothesis: VTS will produce beneficial effects on basic tasks of motor control and abnormal motor symptoms in patients with movement disorders. VTS Settings will include continuous stimulation between 60-120 Hz, intermittent stimulation at  $\frac{1}{2}$  baseline step frequency during walking, and sham stimulation (2 seconds of 30 Hz stimulation only at stimulation onset).

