### **6.2 Participants:**

We will recruit 30 patients with PD who are between the ages of 18-80 years old and independently living in the community. Will additionally recruit up to 5 patients with ET and up to 5 patients with dystonia. To account for screening failures or patients who cannot tolerate the sensory stimulation, we anticipate screening and consenting ~50 individuals.

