### **6.7 Duration of Study and Overview of Procedures and Protocol:**

Testing will occur over the course of a single day at the Fixel Institute for Neurological Diseases. Similar to new patient clinical evaluations, subjects will be instructed to withhold any PD, ET, or dystonia medications for 12 hours prior to testing. The study visit will last up to 4 hours and will include a variety of motor tasks and clinical tests (described in detail below) both on and off VTS. For Parkinson's disease and essential tremor patients, the devices will be worn on the wrist and/or ankles. For patients with dystonia, the devices will be adhered to the skin of the neck using medical grade double sided tape and a latex medical wrap. Patients with PD will undergo a more comprehensive testing evaluation, while patients with ET or dystonia will undergo a brief, more focused evaluation. Subject responses will not be compared across diseases given the preliminary nature of the research and analysis. Outcomes to be measured are described below in the order that they will be tested for each individual subject group (PD, ET, dystonia).

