#### Baseline testing:

MDS-UPDRS: Select measures from the motor section of the Movement Disorders Society Unified Parkinson's Disease Rating Scale (MDS-UPDRs). The MDS-UPDRS is a revision of the Unified Parkinson's Disease Rating Scale (UPDRS) originally developed in the 1980s. The scale is used in the clinic as well as in research to measure PD symptom severity. Individual measures are rated as 0 (normal) to 4 (severe).

Montreal Cognitive Assessment (MoCA): The MoCA is a cognitive screening test designed to assist Health Professionals in the detection of mild cognitive impairment and dementia. It will be used to exclude patients with cognitive impairment significant enough to confound the research variables of interest.

6.7a: Outcomes to be measured in subjects with PD:

Quantitative Tremor Assessment: An external accelerometer (Delsys Trigno; <https://delsys.com/trigno/>) will be adhered to the skin of the dorsum of the hand and will be used to quantify displacement of the hand due to tremor in the settings listed below. Delsys Trigno sensors have been used in multiple prior UF IRB approved studies and is FDA and CE registered with FCC ID, and is certified IEC601-1 (General Requirements for Medical Devices) and IEC601-1-2 (electromagnetic compatibility requirements for Medical Devices) with a UL recognized Internal Battery.

- 1. Sitting at rest
- 2. Sitting with both arms outstretched
- 3. Sitting at rest while performing a distracting cognitive task (reciting the months of the year backwards)
- 4. Transition from rest to posture (arms held directly in front of patient) for 10 seconds

Kinesia One accelerometer: The following select measures of MDS-UPDRS Part III: Motor Examination will be repeated before and during VTS:

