## **7. Outcome and Statistical Approaches:**

For essential tremor and dystonia, the aims of this unblinded pilot study are to identify the optimal settings of VTS that are most promising to be tested in future clinical trials, statistical analysis will be limited to basic measures of central tendency. We will compare scores and values on the individual outcome measures listed above both on and off VTS, and within disease group means for each measure will be used to help guide the choice of settings to be tested in future studies. This pilot study will not be powered for between disease groups analysis or to test the efficacy of VTS for ET, or dystonia.

For Parkinson's disease, we expect to have data sufficient to justify exploratory statistical analysis. We have estimated that the number of patients included will allow for statistical analysis of patient's task performance before and during VTS. This was based on a medium effect size (Cohen's  $d = 0.50$ ) for the comparison of tremor power during VTS versus baseline. With an alpha of 0.05 and power of 0.80, the required sample size is 27 (based on a one-sided paired sample t-test). Thus, by recruiting 30 participants with PD, our sample size will give us sufficient statistical power to detect an effect with medium effect size. Statistical analysis will consist of a repeated measures ANOVA on the change in tasks performance scores relative to baseline. All post-hoc analyses will be corrected for multiple comparisons using Bonferroni correction.

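### Feasibility and reliability are in the only specific aim, but the plan describes no same-setting repeat and no analysis of either, so test-retest reliability cannot be estimated and feasibility has no denominator

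*Combined protocol and SAP*

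**What the plan says.** Section 5 has one aim with three objects: "Evaluate the feasibility, reliability, and clinical effects of VTS". The hypothesis beneath it concerns only beneficial effects, and it lists the active and sham settings.

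Section 6.7 places everything in one session: "Testing will occur over the course of a single day". The visit lasts up to 4 hours and compares performance on and off VTS. For the Kinesia items the plan says: "The following select measures of MDS-UPDRS Part III: Motor Examination will be repeated before and during VTS".

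Section 7 limits ET and dystonia to measures of central tendency. For PD it specifies a "repeated measures ANOVA on the change in tasks performance scores relative to baseline", and the sample size rests on tremor power during VTS versus baseline.

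On numbers, section 6.2 states "We will recruit 30 patients with PD" and "Will additionally recruit up to 5 patients with ET and up to 5 patients with dystonia". It continues: "To account for screening failures or patients who cannot tolerate the sensory stimulation, we anticipate screening and consenting ~50 individuals". Section 9 ends the subject numbering at PD30, ET5 and DYT5. Sections 8 and 10 say that data from patients who stop early can still be of use.

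**The concern.** Two of the three objects of the only aim have no route from measurement to result.

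For reliability, the gap lies in the measurements as well as in the analysis text. A before-and-during pair contrasts two conditions; it does not replicate one. Without a replicate, the study cannot say how much a patient's tremor or tapping score moves with no intervention. It then cannot say which individual changes exceed ordinary variation, or which measures are stable enough for a later trial. Choosing settings for later trials is a stated purpose of this study, and section 6.5 says that the settings of an earlier study of a previous device version were not investigated well enough beforehand.

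For feasibility, inability to tolerate the stimulation is one of the most informative results a wearable stimulator can produce. Here it appears only as a recruitment allowance for "patients who cannot tolerate the sensory stimulation". With no stated denominator, a completion rate could be reported on completers alone.

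**Working it through.** **1. The plan's own figure.** Inputs from section 7: d = 0.50, one-sided alpha 0.05, power 0.80, paired t-test. Power is P(T > t(0.95; n−1)), where T is noncentral t with n−1 degrees of freedom and noncentrality d√n.
- n = 27: critical value 1.706, noncentrality 0.50 × √27 = 2.598, power 0.812.
- n = 26 gives 0.798, so 27 is the smallest sufficient n and the stated figure reproduces.
- n = 30 gives 0.848.

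This calculation covers the VTS-versus-baseline contrast only. Neither feasibility nor reliability has a precision basis.

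**2. Is any condition measured twice under the same setting?**
- Kinesia items: before VTS and during VTS, which are two conditions.
- Quantitative tremor, dexterity and TUG: tested on and off VTS, with no number of repeats per setting.
- Reaction time: the GO-signal delay varies, which suggests several trials. The number is not given and no reliability analysis of them is planned.
- TUG on the gait mat: stride-level quantities within a walk, which are again within-task.
- Sham: 2 seconds of 30 Hz at onset. It is close to an off-VTS measurement but not identical to one.

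No same-setting repeat is described, so a test-retest ICC or within-patient SD cannot be computed from what is described.

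**3. What one repeat would give.** Assume 30 PD patients measured twice under one condition, with a one-way ICC r. Then F = (1 + r)/(1 − r). The limits are F_L = F / F(0.975; 29, 30) and F_U = F × F(0.975; 30, 29), and each converts back as (F − 1)/(F + 1). The two quantiles are 2.083 and 2.092.
- r = 0.80: F = 9.00, F_L = 4.32, F_U = 18.83; 95% interval 0.62 to 0.90.
- r = 0.70: F = 5.67, F_L = 2.72, F_U = 11.86; 95% interval 0.46 to 0.84.

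The values of r are assumptions. The intervals are wide but usable for a pilot.

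**4. How far completion could be overstated.** Places: 30 + 5 + 5 = 40 at most. Extra consents: about 50 − 40 = 10. The plan does not split these between screening failure and intolerance. Let k be the number who received stimulation, could not tolerate it and had their place refilled (assumed, 0 to 10), with all 40 places filled by completers. Completion among everyone stimulated is 40/(40 + k), with exact (Clopper-Pearson) 95% intervals:

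| k | Completion, all stimulated | 95% interval | Completers only | Difference |
|---|---|---|---|---|
| 0 | 40/40 = 100% | 91.2–100 | 100% | 0 points |
| 2 | 40/42 = 95.2% | 83.8–99.4 | 100% | 4.8 points |
| 5 | 40/45 = 88.9% | 75.9–96.3 | 100% | 11.1 points |
| 10 | 40/50 = 80.0% | 66.3–90.0 | 100% | 20.0 points |

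**The case against.** The strongest reply is that this is a self-described pilot with exploratory analysis, and that the documents are silent on repeats rather than ruling them out. Part of that stands. The number of trials per setting is not given and the reaction-time task probably has several, so it would be wrong to say that no repetition of any kind takes place. Trials within one task run show within-session consistency, however, and no analysis of them is planned.

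A reader might infer that, without a replicate, no change from baseline can be told apart from test-retest variation. The documents do not support that at group level. The repeated measures ANOVA uses within-patient residual variation as its error term, and the sham setting offers a comparison in the same patients. The limitation applies to judging individual patients and to the reliability part of the aim. Sham does not fill that gap: it delivers brief stimulation, and section 6.5 reports that a different sham setting in the earlier study appeared to reduce tremor in about 60% of patients.

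A reader might also infer that the feasibility figure will be inflated. The plan sets no denominator and regards partial data as useful, so the inflation is conditional. A PD-only worst case of 30/40 = 75% is tempting too. It requires all of the roughly 10 extra consents to be PD patients and all to be intolerant, although the allowance covers three disease groups and names screening failures as well.

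Finally, reliability in the aim may mean consistency of the response to VTS rather than of the measures. That reading would also need a repeat, and none is described.

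**Conclusion.** The concern holds in this form. The plan as written cannot answer the reliability part of its only aim by test-retest, and it leaves feasibility undefined. The possible overstatement of completion is 0 to 20 percentage points. That range assumes 40 completers, about 50 consents, and that intolerant patients drop out of the denominator; it is zero if all the extra consents are screening failures. The documents do not show that an overstatement will occur, nor that the group-level inference is unsound. The change should be made before testing starts, because a missing repeat cannot be recovered afterwards.

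**What to change.** - **Reliability.** Repeat one short off-VTS block, for example resting tremor and finger tapping, before the first stimulation. Report the ICC and within-patient SD with 95% intervals. Placing it before stimulation matters: a repeat only at the end of the visit would mix measurement error with fatigue, practice, longer time off medication and any carry-over. An optional end-of-visit off-VTS repeat would show drift and carry-over and should be reported separately. If no repeat is added, delete reliability from the aim.
- **Feasibility.** In section 7, define it as completion of all planned settings among everyone who received any stimulation, including patients whose place was refilled, with an exact 95% interval. List screening failures separately from intolerance. Extend the subject numbering in section 9 so that patients beyond the targets can be identified and counted.

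The cost is a few minutes in a visit of up to 4 hours, some wording, and possibly a less favourable feasibility figure. The ANOVA and the sample size of 27 need no change.

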## **6. Research Plan:**

### **6.1 Design Overview:**

This cross-sectional pilot study aims to identify the optimal device settings and preliminarily test the efficacy of the Not Impossible VibroHealth device in improving basic measure of motor control and symptoms in patients with PD and other movement disorders in the off-medication state. After informed consent, screening, and recruitment, the effects of VTS will be evaluated on basic tests of motor control and common movement disorders symptoms.

### **6.2 Participants:**

We will recruit 30 patients with PD who are between the ages of 18-80 years old and independently living in the community. Will additionally recruit up to 5 patients with ET and up to 5 patients with dystonia. To account for screening failures or patients who cannot tolerate the sensory stimulation, we anticipate screening and consenting ~50 individuals.

### **6.3 Recruitment:**

Recruitment will occur exclusively through the UF movement disorders program at the Fixel Institute for Neurological Diseases at UF Health. We expect to recruit patients prior to and during routine scheduled clinic visits with e-consenting (electronic informed consent).

[figure not shown]
## **6.4 Inclusion/Exclusion Criteria:**

### 6.4a. Inclusion criteria:

- Age 18-80 and able to provide informed consent.
- Have a diagnosis of Parkinson's disease, essential tremor, or cervical dystonia made by a movement disorders specialist.
- Medically optimized without planned medication changes for the duration of the study.
- For patients with ET, they will have a score of at least 2 on items 5 and 6 of the Fahn-Tolosa-Marin (FTM) Tremor Rating Scale.
- For patients with dystonia, they will have abnormal dystonic postures of the head and not isolated head tremor

### 6.4b. Exclusion criteria:

- The presence of additional neurologic diseases, that might confound testing or the coexistence of PD and ET together (action tremor that was present prior to the development of parkinsonism).
- Symptoms of peripheral neuropathy at the wrist (reduced vibratory, pinprick, or temperature sensation)
- Montreal cognitive assessment (MoCA) score < 20 or previously documented dementia
- Unable to walk without a walking aid (e.g. cane, stick, walker)

## 6.5 Device Description and Previous Studies

The Vibrohealth system consists of 4 vibrating devices on bands and a magnetic contact charger (**Figure 1**). The devices are paired with a cell phone application (to be used solely by research investigators) that adjusts the parameters of vibratory stimulation during research visits (**Figure 2**).

The device consists of an actuator/sensor that, when placed against the surface of the skin, produces a vibrotactile sensation (vibration) through rapid lateral (side to side) motion. The intensity of the vibration produced by the Vibrohealth device is far less than that produced by commercially available massagers that provide vibratory stimulation for relaxation using similar technology. The sensor in the device is a tri-axial accelerometer and gyroscope that measures position using the same technology as smartphones.

A previous version of the Vibrohealth device was evaluated in 2017-2018 on 52 patients with PD and resting tremor at the Mount Sinai Hospital in New York City in a study funded by the device developer (Not Impossible). The Vibrohealth device was deemed

a nonsignificant risk device and was approved by full board IRB review (IRB #17-00555). There were no adverse events in any subjects receiving VTS. However, the stimulation setting intended to serve as a sham control setting (low amplitude continuous vibration) appeared to reduce resting tremor in approximately 60% of patients, suggesting that the vibration settings used in the protocol were inadequately investigated prior to study design. Though this study is being prepared for publication by the authors at Mount Sinai Hospital as a safety and feasibility study, the Parkinson

Foundation has decided to fund further pilot testing to ensure that any future clinical trials aimed at testing the efficacy of VTS are planned appropriately. We have tested the Vibrohealth device on 7 patients during our initial pilot testing since IRB approval without any adverse events.

#### **6.6 Screening/Baseline Interview and Measures:**

Recruitment will be conducted at the UF Health Fixel Institute for Neurological Diseases via pre-review of outpatient appointments, review of the IRB approved movement disorders database, and during standard of care (SOC) visits. Clinic providers involved with the research study who provide clinical care/intervention for treatment may also discuss the protocol/research with their patient. If participants are identified through pre-review of outpatient records/lists/appointments, providers associated with clinical care for the subject will be notified of the subject's potential availability. No other information will be collected during the pre-screening process. The provider will then mention the study to the patient, if appropriate. When interested, subjects will either contact us about the study or the clinic providers will notify study coordinators of participant interest.

Study personnel will tell the potential participants about the study. The study personnel will consist of the investigators (UF faculty), staff study coordinators, and clinical movement disorders fellows. All study coordinators will be appropriately trained to meet HIPPA and IRB requirements. The pre-screening of records will only be carried out by study coordinators who already have approved EPIC medical record access.

Patients will also be identified using the Fixel Institute for Neurological Diseases patient database (Quantifying Deficits in Patients with Movement Disorders). Patients who have provided informed consent to have their medical information stored in the database and have indicated that they would like to be contacted about future research studies may be contacted (IRB201501166). Potential participants will be identified using database queries including diagnosis, age, location, most recent UPDRS, and most recent clinical visit. These identified potential participants will then be contacted by study coordinators to inform and invite them to participate in this research study.

Once a potential participant's interest in participating in the study is established, the study personnel will read from an approved telephone script to provide details about the study and the inclusion and exclusion criteria. If potential participants are still interested and are eligible to participate in the study, they will then be scheduled for an e-consenting appointment.

